## 2.0 TRIAL DESIGN

### 2.1 Trial Design

This is a two-arm pilot study of High-Intensity Focused Ultrasound (HIFU) and immunotherapy. The goals of the study are to obtain preliminary data on the safety of HIFU with immunotherapy, delivered concurrently, and to obtain preliminary estimates of change in T-cell frequency and activation for HIFU alone (day 15-21 of ARM A) and pembrolizumab and HIFU given in combination (day 15-21 of arm B). The central hypothesis is that focused energy induced immunogenic cell death will overcome limitations in antigen availability, and effective T-cell responses, and thereby enhance immune-therapy of advanced breast cancer. Our secondary hypothesis is that concomitant immune-activation will further augment CD8+ T-cell responses to tumor antigen released by HIFU. We will obtain preliminary data on whether HIFU promotes the presence of CD8+ T-cells in ablated primary tumors, blood and non-ablated distant metastases. Additional correlative science endpoints will be tested as exploratory endpoints.

[figure not shown]
Eligible subjects will be randomized 1:1 to the investigational treatments (Arm A) or (Arm B). Subjects on both arms will undergo HIFU treatment on day 15. Subjects randomized to Arm A will receive pembrolizumab administered IV every 3 weeks on days 22, 43, and 64. Subjects randomized to Arm B will receive pembrolizumab administered IV every 3 weeks on days 1, 22, 43 and 64. In all subjects, restaging breast cancer-dedicated chest, abdomen and pelvic CT scan will be performed at baseline and cycle 4. Biopsies of tumors treated with HIFU will be completed on all patients at days 1 and 22 with optional distant tumor site biopsies and additional biopsies of the HIFU treated breast lesion to be completed at day 64. The tissue removed at the biopsies will be evaluated as part of the immunologic correlative studies.

**Product:** Pembrolizumab

**Protocol/Amendment No.:** UVA Breast 48

V04-13-21

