### 3.2 Secondary Objectives & Hypotheses

**Objective:** To assess the adverse event profile of pembrolizumab and HIFU

**Hypothesis:** The combination of pembrolizumab and HIFU will result in adverse event profiles similar to previously reported profiles for each modality given alone.

**Product:** Pembrolizumab

**Protocol/Amendment No.:** UVA Breast 48

V04-13-21

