#### **5.3 Randomization or Treatment Allocation**

Randomization will be discussed with participants during the process of informed consent and will occur after registration and within 7 days prior to the start of treatment. The randomization codes are generated by the study statisticians and stored in the Cancer Center Clinical Trials Database.

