## 7.2 Assessing and Recording Adverse Events

### 7.2.1 Time Span for Recording Adverse Events

All adverse events that occur after the consent form is signed but before treatment allocation/randomization must be reported by the investigator if they cause the subject to be excluded from the trial, or are the result of a protocol-specified intervention, including but not limited to washout or discontinuation of usual therapy, diet, placebo treatment or a procedure.

From the time of treatment allocation/randomization through 30 days following cessation of treatment, all adverse events must be reported by the investigator. Such events will be recorded at each examination on the Adverse Event case report forms/worksheets. The reporting timeframe for adverse events meeting any serious criteria is described in [Section 7.2.6](#). The investigator will make every attempt to follow all subjects with non-serious adverse events for outcome.

Adverse events will not be collected for subjects during the pre-screening period (for determination of archival tissue status) as long as that subject has not undergone any protocol-specified procedure or intervention. If the subject requires a blood draw, fresh tumor biopsy etc., the subject is first required to provide consent to the main study and AEs will be captured according to guidelines for standard AE reporting.

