	Is an overdose (whether accidental or intentional). Any adverse event associated with an overdose is considered a serious adverse event for collection purposes. An overdose that is not associated with an adverse event is considered a non-serious event of clinical interest and must be reported within 24 hours to the Sponsor and to Merck within 2 working days..	

**Product:** Pembrolizumab

**Protocol/Amendment No.:** UVA Breast 48

V04-13-21

	
Other important medical events that may not result in death, not be life threatening, or not require hospitalization may be considered a serious adverse event when, based upon appropriate medical judgment, the event may jeopardize the subject and may require medical or surgical intervention to prevent one of the outcomes listed previously (designated above by a †).
						
Duration	Record the start and stop dates of the adverse event. If less than 1 day, indicate the appropriate length of time and units						
Action taken	Did the adverse event cause Merck product to be discontinued?						

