Adverse events and DLTs will be summarized by frequency and magnitude for each arm and overall. Change in the proportion of CD8+ to CD4+ tumor infiltrating lymphocytes (TILs) in the primary ablation zone will be estimated by arm. Additionally change in CD8+ T-cell responses at peri-ablation zones and clinical response at local and distant metastatic sites measured by abscopal tumor shrinkage at non-ablated sites, will be estimated for each arm. The Kaplan Meier estimator will be used to estimate survival curves for DFS and OS. Exploratory endpoints including change in T-cells in peripheral blood, markers of T-cell activation, gene expression profiling, and enumeration of myeloid derived suppressor cells will be estimated by arm.

If highly favorable responses are seen in this pilot patient population, then this study may be expanded by means of an amendment to more rigorously define response criteria in either or both arms.

**Product:** Pembrolizumab

**Protocol/Amendment No.:** UVA Breast 48

V04-13-21

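### Adverse events are tabulated only by whole arm and overall, so events before combination exposure are mixed into the totals and the Days 15–21 window is not shown separately

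*Combined protocol and SAP*

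**What the plan says.** Section 8.2 plans a single summary: "Adverse events and DLTs will be summarized by frequency and magnitude for each arm and overall". It gives no period split, no number at risk by period and no use of attribution, and it takes the analysis population as intention to treat. No other section adds a period split.

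Collection starts early. Section 7.2.1 states: "From the time of treatment allocation/randomization through 30 days following cessation of treatment, all adverse events must be reported by the investigator". Under section 5.3, randomisation takes place "within 7 days prior to the start of treatment".

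The schedule in section 2.1 differs by arm before Day 22:
- Both arms: "Subjects on both arms will undergo HIFU treatment on day 15".
- Arm A: "Subjects randomized to Arm A will receive pembrolizumab administered IV every 3 weeks on days 22, 43, and 64".
- Arm B: "Subjects randomized to Arm B will receive pembrolizumab administered IV every 3 weeks on days 1, 22, 43 and 64".

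Section 2.1 makes safety of the two treatments given concurrently a goal of the study. It also identifies Days 15–21 as HIFU alone in Arm A and the combination in Arm B, but only for T-cell change. The safety hypothesis in section 3.2 reads: "The combination of pembrolizumab and HIFU will result in adverse event profiles similar to previously reported profiles for each modality given alone".

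The data needed for a split are collected. Table 7 instructs: "Record the start and stop dates of the adverse event". Section 7.2.3 grades attribution to study drug or HIFU on five levels, and the flow charts in section 6.1 schedule adverse event review on Days 1, 15 and 22 in both arms.

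**The concern.** The safety question is about the combination, which section 4.4 describes as not previously given together in humans. The planned totals answer a different question: what happened to each arm from randomisation onward, whatever the participant had received by then.

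Three things follow.

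1. Arm A's total includes events from Days 1–14, when the only study intervention is the Day 1 biopsy, and from Days 15–21, when pembrolizumab has not been given. Arm B's total includes events before HIFU. The overall row adds these together, and it is the row most likely to be read as the combination's profile.
2. An Arm A participant who leaves before Day 22 never receives the combination but still counts in the overall row.
3. Days 15–21 is the only randomised, concurrent window in which HIFU alone can be set beside HIFU given on pembrolizumab. From Day 22 both arms receive the same treatments. A whole-period count of participants with any event merges this window with about two further months of common treatment, so an acute difference can fade.

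**Working it through.** The plan gives no figure for the adverse event summary, so there is none to reproduce. The check counts days by exposure and then asks how far a whole-period table could hide an acute difference.

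**Inputs.** HIFU on Day 15 in both arms, and first pembrolizumab on Day 22 (Arm A) or Day 1 (Arm B): section 2.1. Collection from randomisation to 30 days after treatment: 7.2.1. Randomisation up to 7 days before treatment: 5.3, with start of treatment read as Day 1. Windows of ±3 days and cycle 8 on Day 148: 6.1. Six participants per arm: 8.2.

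**Exposure by arm**

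| Days | Arm A | Arm B |
|---|---|---|
| 1–14 | no study treatment | pembrolizumab alone |
| 15–21 | HIFU alone | both given |
| 22 on | both given | both given |

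Pre-combination time is 14 + 7 = 21 days in Arm A and 14 days in Arm B.

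**Share of adverse event time before the combination.** Per arm this is pre-combination days divided by total days. Overall, with equal arms, it is (21 + 14) / (2 × total days).

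- Last dose Day 64 plus 30 days (94 days): Arm A 21/94 = 22%; Arm B 14/94 = 15%; overall 35/188 = 18.6%.
- To Day 64 only: overall 35/128 = 27%.
- Eight cycles plus 30 days (148 + 30 = 178 days): overall 35/356 = 10%.
- 94 days plus the maximum 7 days before Day 1: Arm A 28/101 = 28%; Arm B 21/101 = 21%; overall 49/202 = 24%.

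With Day 1 fixed, the ±3 day windows let the pre-combination time run from 18 to 24 days in Arm A (first dose Day 19 to 25) and from 11 to 17 days in Arm B (HIFU Day 12 to 18). A split should therefore use actual dates.

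**Dilution of an acute difference.** The plan gives no background rate, so these are assumptions: a constant background hazard h per week, equal in both arms, and an extra event probability d = 0.20 in Arm B on Days 15–21 only. If w is the background probability of any event over an interval, the arm difference in participants with any event is [1 − (1 − w)(1 − d)] − w = (1 − w)d. Within the window 1 − w = exp(−h); to Day 94 it is exp(−94h/7).

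| h per week | Difference, Days 15–21 | Difference, to Day 94 |
|---|---|---|
| 0.02 | 0.980 × 0.20 = 20 points | 0.764 × 0.20 = 15 points |
| 0.05 | 0.951 × 0.20 = 19 points | 0.511 × 0.20 = 10 points |
| 0.10 | 0.905 × 0.20 = 18 points | 0.261 × 0.20 = 5 points |

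**What the window could show.** With six per arm, 0/6 has a two-sided 95% upper limit of 1 − 0.025^(1/6) = 46%. Fisher's exact test gives p = 0.061 for 0/6 v 4/6 and p = 0.015 for 0/6 v 5/6. Its power for 10% v 50% is about 6%. The window can be described, not tested.

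**The case against.** The strongest reply is that the planned table is a legitimate description of each sequenced regimen in a pilot whose plan disclaims conclusive comparison of the arms. That stands. The proposal is an addition, not a replacement.

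Several stronger readings are tempting, and the documents do not support them.

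- *That 8.2 credits every event to the combination.* It attributes nothing. Section 7.2.3 records attribution to drug or HIFU, and Table 7 has pembrolizumab recorded as unrelated when the participant has not received it, which covers Arm A before Day 22. A DLT is pembrolizumab-related by definition (7.2.10), so Arm A cannot have one before its first dose. What remains is that 8.2 does not use attribution in the summary. Attribution also cannot, by itself, separate a HIFU reaction alone from one on pembrolizumab.
- *That the randomised contrast is lost.* It is unplanned. Start dates let it be rebuilt, and Days 1–14 is a second randomised window (no study treatment v pembrolizumab).
- *That acute HIFU reactions are hidden.* For a specific reaction the by-arm rows would show them. Take the 36% skin irritation and erythema cited in section 4.2.5 for Arm A and an assumed 70% for Arm B. The overall row shows (36 + 70)/2 = 53%, but the arm rows show the full 34 points. Dilution affects any-event and broad category counts, not every row.
- *That 3.2 needs an internal single-modality control.* Its comparison is with externally reported profiles.
- *That combination statements should rest only on time after both treatments.* That would drop Arm A's acute HIFU reactions. It would also keep the Day 22 biopsy events and most of the background: 94 − 21 = 73 of 94 days (78%) in Arm A. Onset period does not establish cause, since section 5.2.2 allows for pembrolizumab events months after the last dose.

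**Conclusion.** The point holds as a gap in the planned summary, not as an error in the design. Section 8.2 mixes events from before combination exposure into the totals that will describe concurrent safety, and it leaves the protocol's own Days 15–21 distinction unused for adverse events.

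On the core schedule plus 30 days, 22% of Arm A's and 15% of Arm B's observation time is affected. The overall share runs from 27% (to Day 64) to 10% (eight cycles plus 30 days), and it shrinks further for participants who continue longer. These are shares of time, not of events. The dilution figures rest on assumed hazards and an assumed 20-point excess; they show a direction and a plausible range, not an expected result.

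The improvement is modest but nearly free. Prespecifying it matters because the trial is open-label (5.2.4), and windows chosen after events are known would carry less weight.

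**What to change.** Keep the by-arm and overall table, and add to section 8.2:

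1. A descriptive table of adverse events by onset period, using actual treatment dates: no study treatment; pembrolizumab alone; HIFU alone; after both have been given. State the number of participants entering each period and show the recorded attribution.
2. The interval from HIFU to the Day 22 dose, by arm, with participant counts and exact 95% intervals, labelled descriptive (about 6 v 6). Say in advance how the interval closes for anyone without a Day 22 dose.
3. In the overall combination summary, separate reporting of participants who never received both modalities and of events with onset before both had been given.

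Do not limit all statements about the combination to the period after both treatments, and leave the DLT stopping rule unchanged.

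The cost is SAP wording and one or two tables. No new data are needed. The price is small counts and wide intervals in each period, which the table should state.

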## **9.0 LABELING, PACKAGING, STORAGE AND RETURN OF CLINICAL SUPPLIES**

### **9.1 Investigational Product and Device**

The investigator shall take responsibility for and shall take all steps to maintain appropriate records and ensure appropriate supply, storage, handling, distribution and usage of investigational product and device in accordance with the protocol and any applicable laws and regulations.

Clinical drug supplies will be provided by Merck as summarized in Table 8.

Table 8: Product Descriptions

Product Name & Potency	Dosage Form
Pembrolizumab 50 mg	Lyophilized Powder for Injection
Pembrolizumab 100 mg/ 4mL	Solution for Injection

Theraclion will provide the Echopulse device and EPacks, a cooling and coupling set that is used to enable wave transmission and to protect the skin during the HIFU treatment. EPacks are composed of a special liquid, tubing and a membrane and are described further in the user manual.

### **9.2 Packaging and Labeling Information**

Clinical supplies (drug and device) will be affixed with a clinical label in accordance with regulatory requirements.

Echopulse and ePack labeling information can be found in the Echopulse user manual.

### **9.3 Clinical Supplies Disclosure**

This trial is open-label; therefore, the subject, the trial site personnel, the Sponsor and/or designee are not blinded to treatment. Drug identity (name, strength) is included in the label text; random code/disclosure envelopes or lists are not provided.

### **9.4 Storage and Handling Requirements**

Clinical supplies must be stored in a secure, limited-access location under the storage conditions specified on the label.

Receipt and dispensing of trial medication must be recorded by an authorized person at the trial site.

Clinical supplies may not be used for any purpose other than that stated in the protocol.

### **9.5 Returns and Reconciliation**

The investigator is responsible for keeping accurate records of the clinical drug supplies received from Merck or designee, the amount dispensed to and returned by the subjects and the amount remaining at the conclusion of the trial.

**Product:** Pembrolizumab

**Protocol/Amendment No.:** UVA Breast 48

V04-13-21

Upon completion or termination of the study, all unused and/or partially used investigational product will be destroyed at the site per institutional policy. It is the Investigator's responsibility to arrange for disposal of all empty containers, provided that procedures for proper disposal have been established according to applicable federal, state, local and institutional guidelines and procedures, and provided that appropriate records of disposal are kept.

## **10.0 ADMINISTRATIVE AND REGULATORY DETAILS**

### **10.1 Study Conduct and Ethical Considerations**

This study will be conducted in accordance with the standards of Good Clinical Practice, all applicable federal, state, and local laws, and in accord with the ethical principles that originated in the Declaration of Helsinki. The Principal Investigator (PI) is responsible for the conduct of the clinical trial at the site and the PI will ensure that staff are trained and carry out the study in accord with the protocol specifications. The PI will ensure that all study site personnel are aware that the study protocol and all data generated are confidential and should not be disclosed to third parties (with the exception of local and national regulatory bodies which require access for oversight purposes).

### **10.2 UVA Institutional Review Board for Health Sciences Research**

The UVA Institutional Review Board for Health Sciences Research (UVA IRB-HSR) will approve all aspects of this study, including the clinical trial protocol, informed consent documents, and patient materials. Modifications to the protocol or consent form will be reviewed and approved by the UVA IRB-HSR prior to implementation, except when necessary to eliminate apparent immediate hazards to the study participants. The study will undergo continuing IRB review based on the level of risk as assessed by the IRB. This review will take place no less than annually. Reporting to the UVA IRB-HSR will occur as specified in [Section 7.2.7](#).

### **10.3 Consent Forms and the Consenting Process**

Consent forms will be written in accord with 21 CFR 50 and will be reviewed and approved by the UVA IRB-HSR prior to use. Participants will be given a consent form to review and a member of the study team will be available to answer any questions. Informed consent will be obtained from each participant prior to conducting any study-specific procedures or administering study drug.

### **10.4 Maintenance of Study Documents**

Study documents and records will be retained in accordance with local IRB requirements and the regulations specified in 21 CFR 312.

### **10.5 Compliance with Trial Registration and Results Posting Requirements**

Under the terms of the Food and Drug Administration Modernization Act (FDAMA) and the Food and Drug Administration Amendments Act (FDAAA), the Sponsor of the trial is solely responsible for determining whether the trial and its results are subject to the requirements for submission to the Clinical Trials Data Bank, <http://www.clinicaltrials.gov>. Information posted will allow subjects to identify potentially appropriate trials for their disease conditions and pursue participation by calling a central contact number for further information on appropriate trial locations and trial site contact information.

**Product:** Pembrolizumab

**Protocol/Amendment No.:** UVA Breast 48

V04-13-21

## **10.6 Data Collection**

Data will be collected using a centralized electronic case report form called **ON-line Clinical Oncology Research Environment = Oncore**.

### **10.6.1 Endpoint Data**

Endpoint data will be collected using HITC IML data forms, participant-specific binders, and the HITC laboratory database.

The HITC laboratory database, which has password-restricted access, is stored on the UVA Health System Computing Services secured server.

## **10.7 Data Safety Monitoring Plan**

The University of Virginia Cancer Center Data and Safety Monitoring Committee (CC DSMC) will provide oversight of the conduct of this study. The CC DSMC will report to the UVA Protocol Review Committee (PRC).

The UVA CC DSMC will review the following:

- All adverse events
- Audit results
- Application of study designed stopping/decision rules
- Whether the study accrual pattern warrants continuation/action
- Protocol violations

## **10.8 DSMC Monitoring Schedule**

The UVA CC DSMC will meet every month for aggregate review of data. Tracking reports of the meetings are available to the PI for review. Issues of immediate concern by the DSMC are brought to the attention of the sponsor (and if appropriate to the PRC and IRB) and a formal response from the sponsor is requested. Per the UVA Cancer Center NIH approved institutional plan, this study will be audited approximately every 6 months.

**Product:** Pembrolizumab

**Protocol/Amendment No.:** UVA Breast 48

V04-13-21

## 11.0 APPENDICES

### 11.1 ECOG Performance Status

Grade	Description
0	Normal activity. Fully active, able to carry on all pre-disease performance without restriction.
1	Symptoms, but ambulatory. Restricted in physically strenuous activity, but ambulatory and able to carry out work of a light or sedentary nature (e.g., light housework, office work).
2	In bed <50% of the time. Ambulatory and capable of all self-care, but unable to carry out any work activities. Up and about more than 50% of waking hours.
3	In bed >50% of the time. Capable of only limited self-care, confined to bed or chair more than 50% of waking hours.
4	100% bedridden. Completely disabled. Cannot carry on any self-care. Totally confined to bed or chair.
5	Dead.

\* As published in Am. J. Clin. Oncol.: *Okern, M.M., Creech, R.H., Tormey, D.C., Horton, J., Davis, T.E., McFadden, E.T., Carbone, P.P.: Toxicity And Response Criteria Of The Eastern Cooperative Oncology Group. Am J Clin Oncol 5:649-655, 1982.* The Eastern Cooperative Oncology Group, Robert Comis M.D., Group Chair.

### 11.2 Common Terminology Criteria for Adverse Events V4.0 (CTCAE)

The descriptions and grading scales found in the revised NCI Common Terminology Criteria for Adverse Events (CTCAE) version 4.0 will be utilized for adverse event reporting. (<http://ctep.cancer.gov/reporting/ctc.html>)

